DSMB	Data and Safety Monitoring Board
ECOG	Eastern Cooperative Oncology Group
H&P	History & Physical Exam
HRPP	Human Research Protections Program
INR	International Normalized Ratio
IV (or iv)	Intravenously
MTD	Maximum Tolerated Dose
NCI	National Cancer Institute
ORR	Overall Response Rate
OS	Overall Survival
PBMCs	Peripheral Blood Mononuclear Cells
PD	Progressive Disease
PFS	Progression Free Survival
p.o.	peros/by mouth/orally
PR	Partial Response
PT	Prothrombin Time
PTT	Partial Thromboplastin Time
SAE	Serious Adverse Event
SD	Stable Disease
SGOT	Serum Glutamic Oxaloacetic Transaminase
SPGT	Serum Glutamic Pyruvic Transaminase
ULN	Upper Limit of Normal
WBC	White Blood Cells

STUDY SCHEMA**STUDY SUMMARY**

Title	Phase II Study of Everolimus (RAD001, Afinitor®) for Children with Recurrent or Progressive Ependymoma
Short Title	Everolimus (RAD001, Afinitor®) for Children with Recurrent or Progressive Ependymoma
Protocol Number	CRAD001CUS224T
Phase	Phase II
Methodology	Single Arm, Open Labeled Clinical Trial
Study Duration	5 years
Study Center(s)	UT Southwestern Medical Center and approved subsites.
Objectives	
 Determine the Objective Response Rate (ORR = Complete Response Rate + Partial Response Rate + Prolonged Stable Disease Rate) following treatment with everolimus for children with recurrent or progressive ependymomas. Determine the duration of response, progression free survival (PFS) and event free survival (EFS) following treatment with everolimus for children with recurrent or progressive ependymomas. Determine safety and tolerability of everolimus among children with recurrent or progressive ependymomas. Descriptive analysis and correlation of response rate to biological markers of mTOR pathway activation, including phosphorylated S6^{235/236}, phosphorylated S6^{240/244}, phosphorylated PRAS40 (pT246), phosphorylated 4EBP1, phosphorylated P70^{S6K}, and PTEN expression.
Number of Subjects	18 Patients
Diagnosis and Main Inclusion Criteria	Recurrent or Progressive Ependymoma
Study Product(s), Dose, Route, Regimen	Everolimus (RAD001, Afinitor®) orally once a day.
Duration of administration	Up to 2 years.
Reference therapy	None

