2.0 STUDY OBJECTIVES

2.1 Primary Objectives

Determine the objective response rate (ORR = Complete Response Rate + Partial Response Rate + Prolonged Stable Disease Rate) following treatment with everolimus for children with recurrent or progressive ependymomas.

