2.3 Endpoints

- 2.3.1 Objective Response Rate = Complete Response Rate + Partial Response Rate + Prolonged Stable Disease Rate.
- 2.3.2 Duration of Response
- 2.3.3 Progression Free Survival

- 2.3.4 Overall Survival
- 2.4.5 Dose limiting toxicities
- 2.4.6 Biological markers of mTOR pathway activation, including phosphorylated S6^{235/236}, phosphorylated S6^{240/244}, phosphorylated 4EBP1, phosphorylated PRAS40 (pT246), phosphorylated P70^{S6K}, and PTEN expression.

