6.0 MEASUREMENT OF EFFECT

6.1 Response Assessment

6.1.1 Definitions

Evaluable for toxicity. All patients will be evaluable for toxicity from the time of their first treatment with study drug.

Evaluable for objective response. Only those patients who have measurable disease present at baseline, have received at least one cycle of therapy, and have had their disease re-evaluated will be considered evaluable for response. These patients will have their response classified according to the definitions stated below. (Note: Patients who exhibit objective disease progression prior to the end of cycle 1 will also be considered evaluable.)

In this study, response and progression will be evaluated using the International Society of Pediatric Oncology Brain, Tumor Subcommittee for the Reporting of Trials criteria shown below with slight modification.³⁴ Response will be assessed by magnetic resonance imaging (MRI) scan every 8 weeks (every 2 cycles) for 1 year, then every 12 weeks.

6.1.2 Complete Response (CR):

Complete disappearance on MRI of all enhancing tumor and mass effect, on a stable or decreasing dose of corticosteroids (or receiving only adrenal replacement doses), accompanied by a stable or improving neurologic examination and must be sustained for at least 4 weeks. If cerebral spinal fluid (CSF) evaluation was positive, it must become negative. CSF negativity has to be confirmed at least two times at consecutive samplings if the CSF was positive.

6.1.3 Partial Response (PR):

Greater than or equal to 50% reduction in tumor size by bi-dimensional measurement on a stable or decreasing dose of corticosteroids, accompanied by a stable or improving neurologic examination and must be sustained for at least 4 weeks.

6.1.4 Minor Response (MR):

Greater than or equal to 25% to < 50% reduction in tumor size by bi-dimensional measurement on a stable or decreasing dose of corticosteroids, accompanied by a stable or improving neurologic examination and must be sustained for at least 4 weeks.

6.1.5 Stable Disease (SD):

Neurologic examination is at least stable and maintenance corticosteroid dose is not increased, and MRI meets neither the criteria for MR nor the criteria for progressive disease and must be sustained for at least 8 weeks.

6.1.6 Stable Disease (SD):

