Neurologic examination is at least stable and maintenance corticosteroid dose is not increased, and MRI meets neither the criteria for MR nor the criteria for progressive disease and must be sustained for at least 8 weeks.

6.1.6.1 Prolonged Stable Disease is defined as stable disease for at least 6 months duration.**6.1.7 Progressive Disease (PD):**

Progressive neurologic abnormalities or worsening neurologic status not explained by causes unrelated to tumor progression (eg, anticonvulsant or corticosteroid toxicity, electrolyte disturbances, sepsis, hyperglycemia, etc), OR a greater than 25% increase in the bi-dimensional measurement on MRI, OR the appearance of a new lesion or new CSF positivity, OR increasing doses of corticosteroids required to maintain stable neurologic status or imaging.

All patients who have measurable disease according to the above response criteria, who received at least 1 cycle of therapy and who have their disease re-evaluated will be evaluable for response. All sites of disease should be followed as either target or nontarget lesions, as categorized at baseline. All measurable lesions up to a maximum of 5 lesions should be identified as target lesions, while all other lesions (either additional measurable lesions or nonmeasurable lesions) should be classified as nontarget lesions. If possible, the same method, radiological or physical, should be employed and assessed by the same individual on each occasion. If possible, the same method should be employed and assessed by the same institution on each occasion. Ideally, any response should be confirmed by repeated evaluation at least 28 days after the first assessment where the response criteria were met.

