6.1.8 Response Review

Patients who have a confirmed response (CR, PR, MR, or prolonged SD) as deemed by the institution will have the response reviewed by an independent expert. Radiological images will be collected only for those patients who require central response review.

6.1.9 Central Review of Imaging:

All required MRIs of the brain and spine with gadolinium contrast will be loaded onto a CD in DICOM format and sent to the address below for central review. Please send an e-mail notification (including tracking number) to the study PI at time of shipping. Note that central review is not required prior to starting therapy, but MRI's should be submitted for central review concurrently with patient enrollment. In the unlikely event that central review does not agree with the local read, the patient will immediately be removed from the protocol and discontinue study drug if study drug had been started. Patients removed from protocol in this fashion will be replaced.

[name]
Department of Pediatrics
[name]
UT Southwestern Medical Center

[name]

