6.1.10 Evaluation of Best Overall Response

The best overall response is the best response recorded from the start of the treatment until disease progression/recurrence (taking as reference for progressive disease the smallest measurements recorded since the treatment started). The patient's best response assignment will depend on the achievement of both measurement and confirmation criteria.

Table 6-1

Target Lesions	Non-Target Lesions	New Lesions	Overall Response	Best Response for this Category Also Requires:
CR	CR	No	CR	>4 wks. confirmation
CR	Non-CR/Non-PD	No	PR	>4 wks. confirmation
PR	Non-PD	No	PR	
SD	Non-PD	No	SD	documented at least once >4 wks. from baseline
PD	Any	Yes or No	PD	no prior SD, PR or CR
Any	PD*	Yes or No	PD	
Any	Any	Yes	PD	

* In exceptional circumstances, unequivocal progression in non-target lesions may be accepted as disease progression.

Note: Patients with a global deterioration of health status requiring discontinuation of treatment without objective evidence of disease progression at that time should be reported as "*symptomatic deterioration*". Every effort should be made to document the objective progression even after discontinuation of treatment.

Note: If subjects respond to treatment and are able to have their disease resected, the patient's response will be assessed prior to the surgery.

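### A minor response reached before six months of stable disease, and held without progression, scores as a primary-endpoint failure on the literal definitions, while six months of no change scores as a success; section 6.1.11 conflicts with that rule.

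*Combined protocol and SAP*

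**What the plan says.** Section 2.1 defines the endpoint as "ORR = Complete Response Rate + Partial Response Rate + Prolonged Stable Disease Rate". The Study Summary, 2.3.1 and 9.1 give the same three components, and MR is not among them.

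Section 6.1.1 says which definitions govern: "These patients will have their response classified according to the definitions stated below". Those definitions set PR at a reduction of 50% or more and make MR a separate class, 25% to <50% (6.1.4). The SD definition (6.1.5, repeated in 6.1.6) requires that the "MRI meets neither the criteria for MR nor the criteria for progressive disease and must be sustained for at least 8 weeks". Section 6.1.6.1 adds: "Prolonged Stable Disease is defined as stable disease for at least 6 months duration".

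Three other places bear on MR:

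- Section 6.1.8 sends to independent review "Patients who have a confirmed response (CR, PR, MR, or prolonged SD) as deemed by the institution". MR is thus called a response, and is listed apart from prolonged SD.
- Table 6-1 (6.1.10) has rows for CR, PR, SD and PD only. Its SD row requires SD to be "documented at least once >4 wks. from baseline".
- Section 6.1.11 measures SD from treatment start until progression. Reaching MR does not end that period.

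Section 9.2 stops the trial if none of the first 7 patients responds, and rejects a 10% ORR if 4 or more of 18 respond.

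**The concern.** An endpoint that credits disease control should not score shrinkage below no change. On the literal definitions it can. The documents give no reason for this, and the wording of 6.1.8 suggests that it was not intended.

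Two things are at stake. A child with lasting shrinkage may count against the drug in a trial where a single patient can settle either decision. And because 6.1.11 can be cited for the opposite scoring, the classification of such a child could be argued after the data are seen.

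**Working it through.** **1. Which children are affected**

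Courses last 28 days, and scans precede courses 3, 5 and 7 (5.2.2), at about days 2×28 = 56, 4×28 = 112 and 6×28 = 168. Each child below is progression-free at six months and never reaches PR, except where stated.

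| Course of disease | Literal 6.1.4–6.1.6 | SD timed by 6.1.11 |
|---|---|---|
| Unchanged for 6 months | success | success |
| MR from the first scan onward | failure | failure, unless MR is treated as SD |
| SD at the first scan, MR later but before 6 months | failure | success can be argued |
| 6 months of SD, then MR | success | success |
| MR, later PR | success | success |

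The second row is the clearest inversion. The third depends on which passage is followed. The last two rows are not in question.

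**2. The plan's own design figures**

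Inputs from 9.2: 7 patients in stage 1, 11 more in stage 2, stop at 0 of 7, reject at 4 or more of 18. With true rate p,

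R(p) = Σ (x = 1 to 7) P[Bin(7, p) = x] × P[Bin(11, p) ≥ 4 − x].

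- p = 0.10: 0.0333 (x = 1) + 0.0375 (x = 2) + 0.0158 (x = 3) + 0.0027 (x ≥ 4) = 0.0893. This is within the stated 10%.
- p = 0.30: 0.1698 + 0.2818 + 0.2224 + 0.1260 = 0.8000. This matches the stated 80%.

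Both stated figures are right for the endpoint as defined.

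**3. How often the two scorings disagree**

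Let p be the literal rate (CR + PR + prolonged SD) and q the rate of durable MR that the literal rule leaves out. The documents give no value for q, so 1, 2.5 and 5 percentage points are assumptions. Any trial that rejects under the literal rule also rejects when durable MR counts, so

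P(final decisions differ) = R(p + q) − R(p).

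At p = 0.10:

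- q = 0.01: 0.1169 − 0.0893, or 0.0275 before rounding
- q = 0.025: 0.1646 − 0.0893, or 0.0752 before rounding
- q = 0.05: 0.2575 − 0.0893 = 0.1682

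For stage 1, P(literal rule stops, wider rule continues) = (1 − p)^7 − (1 − p − q)^7. At p = 0.10 and q = 0.01 this is 0.4783 − 0.4423 = 0.0360.

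| Literal rate p | Final decision differs, q = 1 / 2.5 / 5 points | Stage 1 differs, q = 1 / 2.5 / 5 points |
|---|---|---|
| 10% | 2.8% / 7.5% / 16.8% | 3.6% / 8.6% / 15.8% |
| 20% | 4.1% / 10.0% / 19.1% | 1.8% / 4.2% / 7.6% |
| 30% | 2.3% / 5.3% / 9.4% | 0.8% / 1.9% / 3.3% |

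At q = 0 every entry is zero. These figures set the literal rule against a rule that counts all durable MR. If 6.1.11 is followed instead, only part of q is in dispute.

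**The case against.** The strongest defence is that prolonged SD is a duration criterion, and 6.1.11 is the only passage that says how the duration of SD is measured. Read together, a child with SD at week 8 and MR at week 16 or 24 has SD from treatment start until progression, and so counts. This stands as a tenable reading and narrows the point. It does not help the child in MR at the first scan, who never meets the SD definition, and it contradicts 6.1.5 and 6.1.6 for the others.

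The documents also give little sign that durable MR is common. Section 1.2 reports that in animal models the drug slowed growth more than it shrank tumours. Section 1.3 reports a paediatric phase I study without objective responses, in which one of four ependymomas had prolonged stable disease and three progressed. This does not exclude MR, but neither does it support a rate as high as 5 points.

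A reader might infer more than the text supports:

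- *That every MR held for six months is a failure.* Children who later reach PR, or who complete six months of SD first, already count.
- *That Table 6-1 contradicts the literal rule on MR.* It has no MR row, which is an omission. Its stated mismatch is the time required for SD, more than 4 weeks against at least 8.
- *That day 168 falls short of six calendar months (about 183 days), so that MR first seen before course 9 is also caught.* Section 5.2.2 equates scans every other month with scans before courses 3, 5, 7 and so on, and 4.1 and 4.5 treat 24 courses as two years. On that usage the scan before course 7 is the six-month scan.
- *That the literal rule could inflate a positive result, or that the stated power and type I error are wrong.* The literal rule can only lower the count, and both figures reproduce.

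**Conclusion.** The concern holds in this limited form. On the governing definitions, a child whose best result is MR, reached before six months of SD and held without progression to six months or more, is a failure, while an unchanged tumour is a success. The ordering is plainly wrong for MR from the first scan onward. For MR first seen at a later scan before six months, the protocol supports either scoring.

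The size rests on an assumed durable-MR rate and may be nil. The error is conservative: it can cost a positive result but cannot create one. It should still be fixed, because one patient can settle either decision and the rule can be settled in advance at little cost.

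**What to change.** Before the data are examined:

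1. Define the third ORR component as SD or MR without progression for at least six months. Carry this through the Study Summary, 2.1, 2.3.1, 6.1.4–6.1.6, 6.1.11 and 9.1, and add an MR row to Table 6-1.
2. Name the scan that documents six months. The protocol's use of courses as months points to the scan before course 7.
3. Confirm that the 10% and 30% rates in 9.2 refer to this definition.
4. Tabulate CR, PR, durable MR and prolonged SD separately, and report the 4-of-18 decision with and without durable MR.

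This needs no extra scans or patients if the two rates already refer to the wider definition, and 6.1.8 already sends MR to independent review. The cost lies in step 3. If the 10% null excluded durable MR, a background rate of 1, 2.5 or 5 points would raise the rejection probability from 8.9% to 11.7%, 16.5% or 25.8%, against a stated 10%. In that case, either keep the literal decision as primary, say so in one sentence, align 6.1.11 and Table 6-1 with it and report the wider decision as a sensitivity analysis, or restate the operating characteristics for the wider endpoint. Keeping the literal rule costs only text, but leaves lasting shrinkage scored below no change.

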6.1.8 Response Review

Patients who have a confirmed response (CR, PR, MR, or prolonged SD) as deemed by the institution will have the response reviewed by an independent expert. Radiological images will be collected only for those patients who require central response review.

6.1.9 Central Review of Imaging:

All required MRIs of the brain and spine with gadolinium contrast will be loaded onto a CD in DICOM format and sent to the address below for central review. Please send an e-mail notification (including tracking number) to the study PI at time of shipping. Note that central review is not required prior to starting therapy, but MRI's should be submitted for central review concurrently with patient enrollment. In the unlikely event that central review does not agree with the local read, the patient will immediately be removed from the protocol and discontinue study drug if study drug had been started. Patients removed from protocol in this fashion will be replaced.

[name]
Department of Pediatrics
[name]
UT Southwestern Medical Center

[name]

6.1.10 Evaluation of Best Overall Response

The best overall response is the best response recorded from the start of the treatment until disease progression/recurrence (taking as reference for progressive disease the smallest measurements recorded since the treatment started). The patient's best response assignment will depend on the achievement of both measurement and confirmation criteria.

Table 6-1

Target Lesions	Non-Target Lesions	New Lesions	Overall Response	Best Response for this Category Also Requires:
CR	CR	No	CR	>4 wks. confirmation
CR	Non-CR/Non-PD	No	PR	>4 wks. confirmation
PR	Non-PD	No	PR	
SD	Non-PD	No	SD	documented at least once >4 wks. from baseline
PD	Any	Yes or No	PD	no prior SD, PR or CR
Any	PD*	Yes or No	PD	
Any	Any	Yes	PD	

* In exceptional circumstances, unequivocal progression in non-target lesions may be accepted as disease progression.

Note: Patients with a global deterioration of health status requiring discontinuation of treatment without objective evidence of disease progression at that time should be reported as "*symptomatic deterioration*". Every effort should be made to document the objective progression even after discontinuation of treatment.

Note: If subjects respond to treatment and are able to have their disease resected, the patient's response will be assessed prior to the surgery.

6.1.11 Duration of Response

Duration of overall response: The duration of overall response is measured from the time measurement criteria are met for CR or PR (whichever is first recorded) until the first date that recurrent or progressive disease is objectively documented (taking as reference for progressive disease the smallest measurements recorded since the treatment started).

The duration of overall CR is measured from the time measurement criteria are first met for CR until the first date that recurrent disease is objectively documented.

Duration of stable disease: Stable disease is measured from the start of the treatment until the criteria for progression are met, taking as reference the smallest measurements recorded since the treatment started.

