Table 4-8 Clinically relevant drug interactions: substrates, inducers, inhibitors of PgP and PgP/CYP3A dual inhibitors

Substrates:
digoxin, fexofenadine, indinavir, vincristine, colchicine, topotecan, paclitaxel
Inducers:
rifampin, St John's wort
PgP Inhibitors and PgP/CYP3A Dual Inhibitors:
amiodarone, captopril, carvedilol, clarithromycin, conivaptan, diltiazem, dronedarone, elacridar, erythromycin, felodipine, fexofenadine, ginkgo (ginkgo biloba), indinavir, itraconazole, lopinavir, mibepradil, milk thistle (silybum marianum), nifedipine, nitrendipine, quercetin, quinidine, ranolazine, ritonavir, saquinavir, Schisandra chinensis, St John's wort (hypericum perforatum), talinolol, telmisartan, tipranavir, valspar, verapamil
Reference: Internal Clinical Pharmacology Drug-drug interaction (DDI) memo, updated Oct. 2, 2011, which summarizes DDI data from three sources including the FDA's "Guidance for Industry, Drug Interaction Studies", the University of Washington's Drug Interaction Database, and Indiana University School of Medicine's Drug Interaction Table.

4.6.3 **Vaccinations:** Immunosuppressants may affect the response to vaccination and vaccination during treatment with Everolimus may therefore be less effective. The use of live vaccines should be avoided during treatment with Everolimus. Examples of live vaccines are: intranasal influenza, measles, mumps, rubella, oral polio, BCG, yellow fever, varicella, and TY21a typhoid vaccines.

4.6.4 **Wound healing complications:** Impaired wound healing is a class effect of rapamycin derivatives, including everolimus. Caution should therefore be exercised with the use of Afinitor in the peri-surgical period.

4.6.5 **Prohibited concomitant therapy** Anti-neoplastic therapies: Treatment with systemic anticancer agents (chemotherapy, hormone therapy, targeted or biologic agents) other than the protocol treatment is not permitted until disease progression is documented per RECIST. Palliative radiotherapy or surgery is not allowed.

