5.5 Removal of Subjects from Study

Patients can be taken off the study treatment and/or study at any time at their own request, or they may be withdrawn at the discretion of the investigator for safety, behavioral or administrative reasons. The reason(s) for discontinuation will be documented and may include:

- 5.5.1 Patient voluntarily withdraws from treatment (follow-up permitted);
- 5.5.2 Patient withdraws consent (termination of treatment and follow-up);
- 5.5.3 Patient is unable to comply with protocol requirements;
- 5.5.4 Patient demonstrates disease progression (unless continued treatment with study drug is deemed appropriate at the discretion of the investigator);
- 5.5.5 Patient experiences toxicity that makes continuation in the protocol unsafe;
- 5.5.6 Treating physician judges continuation on the study would not be in the patient's best interest;

- 5.5.7 Patient becomes pregnant (pregnancy to be reported along same timelines as a serious adverse event);
- 5.5.8 Development of second malignancy (except for basal cell carcinoma or squamous cell carcinoma of the skin) that requires treatment, which would interfere with this study;
- 5.5.9 Lost to follow-up: If a research subject cannot be located to document survival after a period of 2 years, the subject may be considered "lost to follow-up." All attempts to contact the subject during the two years must be documented and approved by the Data Monitoring Committee.

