6.1.12 Progression-Free Survival

Progression-free survival (PFS) is defined as the duration of time from start of treatment to time of progression.

6.1.13 **Event-Free Survival**

Event-Free Survival (EFS) is defined as the duration of time from start of treatment to: (1) disease progression; (2) second malignant neoplasm; (3) death regardless of cause; or (4) date of last contact, whichever comes first.

6.2 **Safety/tolerability**

Analyses will be performed for all patients having received at least one dose of study drug. The study will use the CTCAE version 4.03 (download: <http://ctep.cancer.gov/reporting/ctc.html>) for adverse event reporting.

7.0 **ADVERSE EVENTS**

7.1 **Experimental Therapy**

7.1.1

7.2 **Adverse Event Monitoring**

Adverse event data collection and reporting, which are required as part of every clinical trial, are done to ensure the safety of subjects enrolled in the studies as well as those who will enroll in future studies using similar agents. Adverse events are reported in a routine manner at scheduled times during a trial. Additionally, certain adverse events must be reported in an expedited manner to allow for optimal monitoring of the subject's safety and care. Adverse events not requiring expedited reporting will be entered into the eCRF on a monthly basis.

All subjects experiencing an adverse event, regardless of its relationship to study drug, will be monitored until:

- the adverse event resolves or the symptoms or signs that constitute the adverse event return to baseline;
- any abnormal laboratory values have returned to baseline;
- there is a satisfactory explanation other than the study drug for the changes observed; or
- death.

7.2.1 **Definitions**

An adverse event is defined as any untoward or unfavorable medical occurrence in a human research study participant, including any abnormal sign (for example, abnormal physical exam or laboratory finding), symptom, clinical event, or disease, temporarily associated with the subject's participation in the research, whether or not it is considered related to the subject's participation in the research.

Adverse events encompass clinical, physical and psychological harms. Adverse events occur most commonly in the context of biomedical research, although on occasion, they can occur in the context of social and behavioral research. Adverse events may be expected or unexpected.

Severity

Adverse events will be graded by a numerical score according to the defined NCI

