9.2 Sample Size and Accrual

Simon's two-stage optimal design³⁵ is used to compute the number of patients to be recruited for this phase II trial. The null hypothesis that the true objective response rate (ORR) is 10% will be tested against a one-sided alternative. In the first stage, 7 patients will be accrued. If there is no ORR seen in these 7 patients, the study will be stopped.

Otherwise, 11 additional patients will be accrued for a total of 18 patients. The null hypothesis will be rejected if 4 or more ORRs are observed in 18 patients. This design yields a type I error rate of 10% and power of 80% when the true ORR is 30%. It is expected that the accrual will be completed in 2 years since 9 patients are expected to be recruited in a year.

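### Stability recorded after a switch to other anticancer treatment can count as prolonged stable disease, and so as a primary success, because the response windows end only at progression

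*Combined protocol and SAP*

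**What the plan says.** **Endpoint.** Sections 2.1, 2.3.1 and 9.1 define the primary endpoint as complete response plus partial response plus prolonged stable disease. Section 6.1.6.1 sets prolonged stable disease at six months or longer.

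**Windows.** Section 6.1.10: "The best overall response is the best response recorded from the start of the treatment until disease progression/recurrence". Section 6.1.11: "Stable disease is measured from the start of the treatment until the criteria for progression are met". Duration of response (6.1.11) runs to documented recurrence or progression, and PFS (6.1.12) to progression. For EFS, section 6.1.13 reads "Event-Free Survival (EFS) is defined as the duration of time from start of treatment to: (1) disease progression" and goes on to second malignant neoplasm, death from any cause, and date of last contact. Section 9.3 names Kaplan-Meier with Greenwood intervals and gives no censoring rule. None of these sections mentions the start of other anticancer treatment.

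**Resection.** A note in 6.1.10 says: "If subjects respond to treatment and are able to have their disease resected, the patient's response will be assessed prior to the surgery".

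**Prohibitions.** Section 4.6.1 bars other systemic anticancer agents, and 4.6.5 bars them until progression is documented. Section 4.6.5 adds: "Palliative radiotherapy or surgery is not allowed".

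**Leaving treatment without progression.** Sections 4.8 and 5.5 allow it for toxicity, intercurrent illness, investigator judgement or voluntary withdrawal, the last with follow-up still permitted. Appendix II has a long-term follow-up row for survival and other treatment.

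**The concern.** In a single-arm trial, six months without growth is read as evidence of drug activity. That reading fails if part of the six months was spent on something else. The stable-disease clock starts with everolimus but does not require the child to remain on it.

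Take a child who stops at month 2 with stable disease because of toxicity, starts radiotherapy or chemotherapy, and has a scan at month 6 showing no progression. As the text stands, that child has prolonged stable disease and counts toward the four successes needed. Section 1.1 itself reports long-term survivors after a second course of radiotherapy at recurrence, so the possibility is not fanciful. The error can only add successes.

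The resection note covers part of this. It fixes response status before surgery, but for subjects who respond. It does not say whether a child with stable disease is included, and it does not stop the clocks for duration of response, PFS or EFS.

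**Working it through.** **1. Does the route exist in the text?** Three conditions are needed.

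- *A child can be off everolimus, unprogressed and still followed.* Yes: 4.8, 5.5 and the discontinuation rules in Tables 4-1 to 4-3 and 4-6.
- *Other treatment can start before progression.* While the child is on protocol, only as a deviation from 4.6.1 or 4.6.5. Those sections govern conduct; neither says how a child who receives such treatment is analysed.
- *A later scan can count.* Nothing excludes it. Few such scans are scheduled, however: section 5.2.2 places MRIs before set courses and at the end of treatment, and follow-up afterwards is for survival by phone or record review (4.9, Appendix II). A scan at month 6 in a child who stopped at month 2 would be unscheduled. In a child who stops nearer month 6, the Appendix II end-of-treatment visit may fall up to 30 days after stopping, so its MRI could come after new treatment has begun.

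The route is therefore open but narrow.

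**2. Reproduce the design (section 9.2).** The inputs are 7 patients in stage 1, 11 more in stage 2, and rejection at 4 or more of 18. On the null, "The null hypothesis that the true objective response rate (ORR) is 10% will be tested against a one-sided alternative"; on stage 1, "If there is no ORR seen in these 7 patients, the study will be stopped". With X1 ~ Bin(7, p) and X2 ~ Bin(11, p):

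P(reject) = Σ over x = 1 to 7 of P(X1 = x) × P(X2 ≥ 4 − x)

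At p = 0.10:

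- x = 1: 0.3720 × 0.0896 = 0.0333
- x = 2: 0.1240 × 0.3026 = 0.0375
- x = 3: 0.0230 × 0.6862 = 0.0158
- x ≥ 4: 0.0027

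The total is 0.0893, within the stated 10% ceiling. At p = 0.30 the same sum gives 0.800, the stated power. The design is sound as computed.

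**3. How often is the result one child short?** P(exactly 3 of 18, stage 1 passed | 0.10) = Σ over x = 1 to 3 of P(X1 = x) × P(X2 = 3 − x) = 0.3720 × 0.2131 + 0.1240 × 0.3835 + 0.0230 × 0.3138 = 0.134. In that case one reclassified child turns a negative trial positive: 3/18 (exact 95% CI 3.6% to 41.4%) becomes 4/18 (6.4% to 47.6%).

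**4. False-positive rate with one affected child.** Let that child count as a success with probability q instead of 0.10, the other 17 staying at 0.10. The child falls in stage 1 with chance 7/18, giving X1 = Bin(6, 0.10) + Bernoulli(q). Otherwise, with chance 11/18, X2 = Bin(10, 0.10) + Bernoulli(q).

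| q (assumed) | Child in stage 1 | Child in stage 2 | Weighted 7/18, 11/18 |
|---|---|---|---|
| 0.10 (no effect) | 8.9% | 8.9% | 8.9% |
| 0.20 | 10.6% | 10.2% | 10.4% |
| 0.30 | 12.2% | 11.5% | 11.8% |
| 0.40 | 13.9% | 12.8% | 13.2% |
| 0.80 | 20.5% | 17.9% | 18.9% |

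With two affected children the weighted figure is 18.6% at q = 0.40 and 35.0% at q = 0.80. The documents give neither a rate of switching before progression nor a success rate after it, so every row above 0.10 is an assumption.

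**The case against.** The strongest reply is that the protocol already closes the main route. Other systemic agents are barred before progression, palliative radiotherapy and surgery are barred, and treatment given after progression cannot affect any of these endpoints. Stable disease is not a default status: section 6.1.5 requires an MRI finding, an at least stable neurologic examination and no corticosteroid increase. An institution's call of prolonged stable disease also goes to independent review (6.1.8). Most of this stands, and it limits how many children could be affected. It does not remove the gap, because neither the prohibitions nor the review say whether a scan taken after a switch is admissible.

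A reader might infer three stronger things that the documents do not support:

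- *That no endpoint has a cut-off at resection.* Response status has one in the 6.1.10 note, at least for subjects who respond.
- *That the plan credits rescue treatment to everolimus by design.* It can do so only for children who are off drug without progression, or through deviations.
- *That the false-positive rate is 19% to 35%.* Those figures need one or two affected children with an 80% chance of success. Section 1.1 mentions survivors after re-irradiation, but also says chemotherapy responses seldom last. At 20% to 30%, one child gives 10.4% to 11.8%, close to the nominal 10%.

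It is also fair to say that following PFS and EFS regardless of later treatment is a recognised choice, that censoring at a switch can be informative, and that these endpoints are secondary and reported descriptively. Finally, the word palliative in 4.6.5 may govern both radiotherapy and surgery, so its tension with the resection note is an ambiguity rather than a proven contradiction.

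**Conclusion.** The point holds for the primary endpoint. As written, stability observed after other anticancer treatment has begun can count as prolonged stable disease. The bias can only favour the drug, and the 4-of-18 threshold leaves little room: one child decides the trial in 13.4% of runs at a true rate of 10%. The likely size is modest. One affected child moves the false-positive rate from 8.9% to between 10.4% and 18.9% over assumed success chances of 20% to 80%, and the number of such children is unknown and probably small.

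For duration of response, PFS and EFS, the missing rule is a matter for a sensitivity analysis, not an error in the definitions. The change should be made before results are known, because a ruling on a single child afterwards could settle the trial's conclusion.

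**What to change.** 1. In 6.1.10 and 6.1.11, state that complete response, partial response and prolonged stable disease are assessed only on MRIs done before the first non-protocol anticancer treatment (systemic agent, radiotherapy or tumour resection). A child who has met none of these criteria by then is a non-responder.
2. In 9.3, keep the stated definitions of duration of response, PFS and EFS, and add a sensitivity analysis that ends observation at the last MRI before such treatment. Tabulate the affected children with the date and type of treatment; the other-treatment row in Appendix II provides a place to collect this.
3. Reconcile the resection note in 6.1.10 with the surgery statement in 4.6.5, and say whether the note covers children with stable disease.

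**Cost:** definition wording and one extra tabulation, with no new procedure and no extra patients. The response rate may come out slightly less favourable.
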